4 STUDY DESIGN AND ENDPOINTS

4.1 DESCRIPTION OF THE STUDY DESIGN

This is a phase 2, prospective, randomized, triple-blinded, placebo-controlled study of IL-1RA treatment in patients with acute ACL tear and painful effusions. The study population will include up to 40 participants within 28 days of injury. The study is open to male and female participants who are between the ages of 14 and 40, who have ACL tears. Once enrolled will be randomized into 2 groups (20 subjects per group).

- **Group 1** will receive intra-articular injection of Anakinra (Kineret®, IL-1ra; 150mg) 1-28 days after ACL injury.
- **Group 2** will receive intra-articular injection of saline placebo 1-28 days after ACL injury.

4.2 STUDY ENDPOINTS

4.2.1 PRIMARY ENDPOINT

Patient reported outcomes as measured by KOOS-Symptoms

4.2.2 SECONDARY ENDPOINTS

KOOS QOL, KOOS-pain, KOOS-Sports/Rec, Biomarker levels in synovial fluid, serum and urine at time of surgery MRI T1rho changes at 2 years

5 STUDY ENROLLMENT AND WITHDRAWAL

5.1 PARTICIPANT INCLUSION CRITERIA

In order to be eligible to participate in this study, an individual must meet all of the following criteria:

- Isolated Acute ACL Tear (1-28 days post injury) and painful effusion, with no more than a clinical grade 2 MCL injury.
- Provision of signed and dated combined informed consent/HIPAA form and if a minor, a signed assent.
- Stated willingness to comply with all study procedures and availability for the duration of
- the study
- Male or female, aged 14-40 years
- For females of reproductive potential: use of highly effective contraception.
- Currently participating in a sporting activity
- Documentation of closed growth plates as noted on the screening x-ray

5.2 PARTICIPANT EXCLUSION CRITERIA

An individual who meets any of the following criteria will be excluded from participation in the study:

- History of underlying inflammatory disease (i.e. Rheumatoid Arthritis, Psoriatic Arthritis etc.)
- History of having been diagnosed with hepatitis B or tuberculosis
- Currently have an infections, including infection of the skin, or have signs and symptoms of an infection, including fever.
- History any abnormalities in their white blood cell counts
- History of having a disease that weakens your immune system such as diabetes, cancer, HIV or AIDs
- History of other major medical condition requiring treatment with immunosuppressant or modulating drugs.

- A history of chronic use of non-steroidal anti-inflammatory drugs
- Currently taking immunosuppressant medication, including oral and parenteral corticosteroids (topical and stable dose inhaled corticosteroids are acceptable)
- Females who are pregnant or breastfeeding
- Received a "live" vaccine (smallpox, MMR (measles, mumps and rubella), flu, polio, typhoid, chicken pox, yellow fever, herpes zoster) 1 week prior to screening or are scheduled to receive a "live" vaccine within 1 week after study injection.
- History of bleeding disorders or are taking any blood thinning medications, aspirin or other medications affecting blood clotting.
- Previous exposure or allergic reaction to anakinra
- Allergy to latex or tape
- Allergy to Kineret or have had a reaction to any local or general anesthesia
- Prior ipsilateral knee surgery
- Complete ligament tear other than the ACL
- Received any investigational drug with 4 weeks of study Visit 1
- Does not have the cognitive ability to provide informed consent.

5.3 STRATEGIES FOR RECRUITMENT AND RETENTION

Participants in this trial will be recruited within 28 days from injury following a clinical appointment with one of the study's participating orthopaedic surgeons.

Participants in this trial will be recruited within 28 days from injury from the Emergency Department or walk-in clinics for acute injuries.

No prisoners will be enrolled into the study.

We will enroll children between the ages of 14-17. Parental consent will be needed in order to enroll children into the study.

Participants will receive \$150.00 for taking part in this study. The participant will receive \$50.00 for each MRI they complete (Visit 1, Visit 5, and Visit 6). Payment will be in the form of a check which will be mailed approximately four to six weeks following the study visit. If the participant is a minor the compensation will be mailed to the minor.

Advertising may be used to promote this study to the public. All advertisements and public marketing will be approved by the IRB prior to use.

5.4 PARTICIPANT WITHDRAWAL OR TERMINATION

5.4.1 REASONS FOR WITHDRAWAL OR TERMINATION

Subjects are free to withdraw from participation in the study at any time upon request. An investigator may terminate participation in the study if:

• Any clinical adverse event (AE), laboratory abnormality, or other medical condition or situation occurs such that continued participation in the study would not be in the best interest of the participant

• The participant meets an exclusion criterion (either newly developed or not previously recognized) that precludes further study participation.

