	 Local intolerance of the administered Anakinra (Kineret®) or any sign of allergic response. Development of signs and symptoms before the second time point preventing the second administration of the study drug. Any patient reported and drug related SAE after the first or second administration of the study drug. Diagnosis with any condition as outlined in the exclusion criteria during the course of the initial 2 weeks of study enrollment.
Population:	The study population will include up to 40 subjects within 28 days following of injury. The study is open to male and female participants who are between the ages of 14 and 40, who have ACL tears. Participants will be enrolled at the University of Kentucky.

Phase:	2
Number of Sites enrolling	1 (University of Kentucky)
participants:	
Description of Study	IL-1ra (Kineret®, anakinra), supplied by Sobi Pharmaceuticals, is a
Agent :	recombinant, nonglycosylated form of human interleukin-1 receptor antagonist (IL-1Ra). Kineret® consists of 153 amino acids and has a molecular weight of 17.3 kilodaltons. It is produced by recombinant DNA technology using an E coli bacterial expression system. It is available as pre-filled syringes (100 mg in 0.67 mls) and is FDA approved for daily subcutaneous injection (100 mg/day) for treatment of rheumatoid arthritis (age > 10). A total of 1.5 ml (150 mg) will be injected intra-articularly after synovial fluid aspiration 'to dryness' once between 1 and 28 days after ACL injury.
Study Duration:	24-36 months
Participant	2 years
Duration:	•

SCHEMATIC OF STUDY DESIGN

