2.3 POTENTIAL RISKS AND BENEFITS

2.3.1 KNOWN POTENTIAL RISKS

Safety Precautions: Participants will be followed at regular intervals by their study doctor. During each visit participants will be evaluated for adverse events according to GCP guidelines and reported accordingly to IRB and FDA regulations.

Risks associated with Kineret®:

Reproductive Risks: It is not known whether receiving Kineret® is harmful to an unborn child. Pregnancy after administration of Kineret® may involve risks to the mother, and her embryo or fetus. Therefore, females who are capable of reproducing, must use effective contraceptive methods. These methods must be used from the time of screening until Visit 2 during which any remaining medication will be washed out of the joint during the surgery. If the participant does not elect to have surgery (visit 2) contraception methods will be documented until the end of the study. Examples of effective birth control are: hormonal contraceptives (the pill, implant, transdermal patch, or injection), barrier methods (condom with spermicide, diaphragm with spermicide), IUD, or a male partner had a vasectomy.

Lactating women: It is not known whether this drug or its metabolites are excreted in human milk. Because many drugs are excreted in human milk, caution should be exercised when Kineret® is administered to a nursing woman.

Limitations, potential problems, and alternatives: This study will allow for safety and efficacy assessment in patients with acute effusive knee injury.

- Dose: Based on our work and the work of others, we believe 150 mg dosage is appropriate. The goal of the study is to sustain levels of IL-1Ra long enough and a high enough concentrations during the critical, early time period to be effective. For this reason, we have increased our dosage from a single injection (carried out in the preliminary study) to two injections.
- Patient attrition: Close and regular communication, particularly in the intensive first few months, will be provided to all subject participants. Patients will be fully informed of the time commitments and need for a total of three arthrocenteses in order to recruit study subjects willing to participate in the full study. Because arthrocentesis alone can be expected to benefit subjects, education regarding direct and indirect benefits of all aspects of the trial will be provided. Subjects will also receive appropriate compensation for the time and travel.

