5.5 PREMATURE TERMINATION OR SUSPENSION OF STUDY

This study may be temporarily suspended or prematurely terminated if there is sufficient reasonable cause. Written notification, documenting the reason for study suspension or termination, will be provided by the suspending or terminating party. If the study is prematurely terminated or suspended, the PI will promptly inform the IRB and will provide the reason(s) for the termination or suspension.

Circumstances that may warrant termination or suspension include the above mentioned stopping criteria as well as:

- Determination of unexpected, significant, or unacceptable risk to participants
- Demonstration of efficacy that would warrant stopping
- Insufficient compliance to protocol requirements
- Data that are not sufficiently complete and/or evaluable
- Determination of futility

Study may resume once concerns about safety, protocol compliance, data quality are addressed and satisfy the sponsor, IRB and/or FDA.

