8.5 STUDY HALTING RULES

Administration of study agent will be halted when three grade 3 AEs determined to be "probably related" are reported to the FDA/IRB and enrollment screens will stop accepting new study participants. The study sponsor will inform the DSMB members within 24 hours of this occurrence and will provide the DSMB with AE listing reports. The DSMB will convene an ad hoc meeting by teleconference or in writing as soon as possible. The DSMB will provide recommendations for proceeding with the study to the study sponsor. The study sponsor will inform the FDA of the temporary halt and the disposition of the study.

Study Stopping Criteria

- Local intolerance of the administered Kineret or any sign of allergic response.
- Development of signs and symptoms before the second time point preventing the second administration of the study drug.
- Any patient reported drug related SAE after the first or second administration of the study drug.
- Diagnosis with any condition as outlined in the exclusion criteria during the course of the initial 2 weeks of study enrollment.

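### Section 5.4.1 lets the investigator end participation at any time for a later-met exclusion criterion, and no text keeps that participant in outcome follow-up or, early on, in the analysis

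*Combined protocol and SAP*

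**What the plan says.** Section 5.4.1 introduces its list with "An investigator may terminate participation in the study if". The second item reads "The participant meets an exclusion criterion (either newly developed or not previously recognized) that precludes further study participation". No time window is given, and no section says which of the 5.2 criteria preclude further participation.

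The Protocol Summary, 8.5 and 10.1.2 each carry a list headed as study stopping criteria. One line in all three is "Diagnosis with any condition as outlined in the exclusion criteria during the course of the initial 2 weeks of study enrollment". The line is worded for an individual participant, but 5.5 uses the list for the study as a whole: "Circumstances that may warrant termination or suspension include the above mentioned stopping criteria as well as".

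On dosing, the Protocol Summary has the injection given "once between 1 and 28 days after ACL injury", and the schedule table in 7.3.2 marks administration at Visit 1 only. Other text differs. Section 2.3.1 says "we have increased our dosage from a single injection (carried out in the preliminary study) to two injections", 7.3.1 speaks of a first dose, and the stopping criteria refer to a second administration.

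On what follows a discontinuation, 5.4.2, 6.1.9 and 10.2.1 say that anyone who leaves before a 3-month visit is left out of the analysis and replaced. The schedule has no 3-month visit. Section 8.4.1 provides 30 days of toxicity follow-up after treatment. Section 8.3 collects adverse events for 7 days, and serious ones for 30 days, after the last day of participation. No section provides KOOS, MRI or biomarker collection once participation has been terminated.

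**The concern.** The list in 5.2 was written to decide who enters. Used as a list of reasons to leave, it covers events that can arise over two years in a young, active, mostly operated population: an infection, pregnancy, a corticosteroid course, or "taking any blood thinning medications, aspirin or other medications affecting blood clotting". Some of these could be related to the study drug (infection) or to how the knee is recovering (drug use). Whether such an event ends participation is left to the investigator, because the qualifier on preclusion is undefined.

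The outcome that the trial is sized on is measured one year after surgery. A participant terminated before then has no one-year value, and 10.1.1 gives no method for missing values. If terminations differ between arms in number, or in the kind of patient lost, the comparison of those who remain is no longer the randomised one. With 16 to 20 per group, a few patients are enough to matter.

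There is also a practical problem. Faced with, say, an infection at month 4, a site reads a permissive rule in 5.4.1 and a 2-week line elsewhere, and cannot tell which governs.

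**Working it through.** The main check is textual.

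1. **Window.** 5.4.1: none. Protocol Summary, 8.5 and 10.1.2: the first 2 weeks.
2. **Level.** 5.4.1: the participant. Stopping criteria: headed as study stopping and used at study level in 5.5, but worded per participant. The two rules may conflict or may act at different levels; the documents do not settle it.
3. **Force.** 5.4.1 is permissive and limited to a criterion that precludes participation.
4. **What termination removes.** With the Visit 1 injection of the schedule, a later termination stops no dosing. It ends questionnaires, MRI, blood and urine sampling and any remaining study aspiration (Visits 2 and 3). If there were a second early dose, nearly all of the two years would still come after dosing.
5. **Effect on the analysis.** Before the 3-month visit: excluded and replaced. Between then and Visit 5: no one-year value and no stated missing-data method. After Visit 5: the one-year value is kept and only the 24-month data are lost.

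The plan states no termination rate, so the arithmetic only illustrates. Let p1 and p2 be the fractions lost in the two arms, and let the gap be the mean of retained minus the mean of lost participants, taken as equal in both arms. Each retained mean then exceeds its full-arm mean by p × gap, so:

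shift in the difference = (p2 − p1) × gap

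Inputs from 10.1.1: SD of one-year KOOS Quality of Life scores 24.2; assumed SD of change 0.2 × 24.2 = 4.84, given there as 4.8; target difference 7.2. The loss rates and the gaps are assumptions.

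| Loss, arm 1 vs arm 2 | Gap (points) | Shift (points) | Share of 7.2 |
|---|---|---|---|
| 5% vs 15% | 24.2 | 0.10 × 24.2 = 2.42 | 34% |
| 5% vs 20% | 24.2 | 0.15 × 24.2 = 3.63 | 50% |
| 5% vs 15% | 4.8 | 0.10 × 4.8 = 0.48 | 7% |
| 5% vs 20% | 4.8 | 0.15 × 4.8 = 0.72 | 10% |
| 0% vs 10% | 5 | 0.10 × 5 = 0.5 | 7% |
| 0% vs 20% | 20 | 0.20 × 20 = 4.0 | 56% |
| equal | equal | 0 | 0% |

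At 20 per arm, 5% is one patient and 15–20% is three or four. Equal loss with an equal gap costs only precision: the step from 16 to 20 per group absorbs four losses per arm from all causes together.

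**The case against.** The strongest reply is that 5.4.1 orders nothing. It says the investigator may act, and only on a criterion that precludes participation. The investigator is meant to be blinded, so loss need not differ by arm. This stands, and it is why the point is a risk and not a demonstrated bias.

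A reader might infer from 5.2 that every operated patient becomes terminable at Visit 2, since "Prior ipsilateral knee surgery" is on the list, or that every dosed active-arm patient does, since previous exposure to anakinra is too. The documents do not support this. Surgery is part of the planned path and Visits 3 to 6 are timed from Visit 2, so neither planned surgery nor the study injection can sensibly preclude participation. What remains is that only an undefined phrase rules out the literal reading.

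A reader might also infer a flat contradiction between the 2-week line and 5.4.1. Section 5.5 allows both to hold, one for the study and one for the participant. The defect is the unclear level.

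Some examples are partly covered elsewhere. Section 7.6 allows corticosteroids and clotting drugs if the principal investigator approves, and 8.4.5 deals with pregnancy; neither requires termination. Termination does not end all safety data (8.3, 8.4.1), and because participation includes aspirations and blood draws, some terminations may serve the participant. A fix must leave room for that.

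The size is fragile. The SD of 24.2 belongs to KOOS Quality of Life, whereas the primary endpoint is KOOS-Symptoms, and the plan's own change-score SD cuts the shift to 0.5–0.7 points.

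**Conclusion.** The point holds as a gap in the plan. For two years 5.4.1 permits discretionary termination on an undefined subset of entry criteria. Nearly all such terminations would remove no drug exposure, on the single-injection reading that most of the text supports. No text preserves outcome follow-up for these participants, and early ones are dropped from the analysis and replaced.

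The risk is selective loss after randomisation, and its size is unknown. Under unequal losses of 5% and 15–20% with a 24.2-point gap, the shift is 2.4–3.6 points, or 34–50% of the 7.2-point target. Milder assumptions give about 0.5 points, and equal loss with an equal gap gives none. All of these rest on assumed rates and gaps and, for the larger figures, on the SD of a different KOOS subscale. The documents do not show that loss will be selective.

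The change is worth making because it is cheap and closes a route to bias in a small trial. The number of injections is a separate inconsistency that the sponsor must reconcile; the conclusion here does not depend on it.

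**What to change.** In 5.4.1 and 5.4.2, separate ending study treatment or invasive study procedures from ending follow-up. State that:

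- after randomisation, a newly met or newly recognised exclusion criterion is recorded;
- questionnaires and adverse-event follow-up continue, with biomarkers and MRI where not contraindicated, unless consent is withdrawn or the best-interest item in 5.4.1 applies;
- the participant stays in the analysis as randomised.

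Amend the drop-and-replace sentence in 5.4.2, 6.1.9 and 10.2.1 to match; otherwise it would undo the last item. Ask the sponsor to reconcile the 2-week line in the Protocol Summary, 8.5 and 10.1.2 with 5.4.1, and to say whether that line acts on the participant or the study. Which clinical rule should apply is for the sponsor to settle.

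The cost is a few sentences in 5.4.1 and 5.4.2, plus alignment of three repeated sentences and three repeated bullets. The visits are already scheduled. The drawback is that a few participants with off-criteria conditions stay in the analysis; a sensitivity analysis without them can show whether they matter.

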5.4.2 HANDLING OF PARTICIPANT WITHDRAWALS OR TERMINATION

A subject may withdraw from the study at any time at his or her own request, or may be withdrawn at any time at the discretion of the Investigator for due to safety or scientific reasons. Reasons for discontinuation from the study at any time point will be collected. If subject discontinues the study for any reason prior to 3-month visit, then the collected data will be evaluated but not included in the analysis and a replacement subject will be enrolled in the study.

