6.1.9 DURATION OF THERAPY

Enrolled participants will receive, based on their randomization, either Kineret or a matching saline placebo within 1-28 days after suffering an ACL injury.

If a participant discontinues the study for any reason prior to 3-month visit, then the collected data will be evaluated but not included in the analysis and a replacement participant will be enrolled in the study.

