7.3 STUDY SCHEDULE

7.3.1 SCREENING/ENROLLMENT

Visit 1 Screening 1-28 days following injury)

- Obtain informed consent and assent, if necessary, of potential subjects
- Review medical history to determine eligibility based on inclusion/exclusion criteria.
- Review medication history to determine eligibility based on inclusion/exclusion criteria.
- Perform medical examinations and collect vital signs as needed to determine eligibility based on inclusion/exclusion criteria. All subjects must have a clinical exam that is consistent with an ACL tear.
- Collection of urine and blood for laboratory testing. Women of child bearing potential will be given a urine pregnancy test. Test must be negative in order to enroll into the study.
- Subjects will have the following assessments: range of motion, knee instability (Lachman's test) and standardized MTP-2 weight bearing x-rays.
- Standard questionnaires including the KOOS, IKDC, VR-12 and a Likert pain scale.
- Research knee MRI

Following the review of above assessment results and a review of inclusion/eclusion criteria, subjects will be randomized into 1 of 3 treatment groups. Following randomizing, subjects will undergo a knee aspiration and will receive their first dose study medication.

Visit 2 (day of surgery or 4-6 weeks post injury)

- Knee aspiration (in the operating room under anesthesia)
- Patient reported outcomes (PROs) administered prior to surgery
- KOOS, IKDC, VR-12 and a Likert pain scale administered prior to surgery
- Biomarkers (urine and blood) pre-operatively
- Review for AE's and SAE's
- ROM will be performed prior to surgery

Visit 3 (4-14 days After Visit 2)

- Knee aspiration (if clinically indicated)
- Biomarkers (urine and blood)
- Review for AE's and SAE's
- ROM will be performed

Visit 4 (6 month After Visit 2+/- 2 weeks)

- Patient reported outcomes (PROs) administered
- KOOS, IKDC, VR-12 and a Likert pain scale administered
- Review for AE's and SAE's

• ROM will be performed

Visit 5 (12 monthsAfter Visit 2+/- 2 weeks)

- ÀRI
- Patient reported outcomes (PROs) administered
- KOOS, IKDC, VR-12 and a Likert pain scale administered
- Biomarkers (serum and urine only)
- Review for AE's and SAE's
- ROM will be performed

Visit 6 (24 month After Visit 2+/- 2 weeks)

- MRI
- Patient reported outcomes (PROs) administered
- KOOS, IKDC, VR-12 and a Likert pain scale administered
- Biomarkers (serum and urine only)
- Review for ÀE's and SAE's
- ROM will be performed

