10.2 MEASURES TO MINIMIZE BIAS

10.2.1 ENROLLMENT/ RANDOMIZATION/ MASKING PROCEDURES

Randomization: Following informed consent and after successfully being screened into the study, subjects will be randomized to one of three treatment groups.

- **Group 1** will receive intra-articular injection of Anakinra (Kineret®, IL-1ra; 150mg) 1-28 days after ACL injury.
- **Group 2** will receive intra-articular injection of saline placebo 1-28 days after ACL injury.

Blinding: To ensure triple-blindness, an uninvolved third party will generate the allocation sequence of the intervention and provide this to the principal investigator. Allocation of drug or placebo will be by permutated random block size, ensuring that approximately equal numbers of subjects will be treated with drug or placebo in the unlikely event that the study will need to be terminated prematurely.

If subject discontinues the study for any reason prior to 3-month visit, then the collected data will be evaluated but not included in the analysis and a replacement subject will be enrolled in the study.

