10.2.3 BREAKING THE STUDY BLIND/PARTICIPANT CODE

Breaking the randomization code will be performed by the Principal Investigator and will occur if it is necessary for the care of the subjects. For example, if an AE or SAE occurs with the a subject and knowledge of the drug randomization would be important for clinical care or to determine appropriate treatment, then the principal investigator will break the code and the subject will be withdrawn from the study.

Unblinding of a subject(s) dosing will be documented and will include an explanation of why the study medication was unblinded.

Following data lock, subject dosing information can be unblinded and the unblinded information can be sent to the study participants at the discretion of the principal investigator.

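### Randomised patients who leave before an unscheduled 3-month visit are excluded from the analysis and replaced, with no all-randomised set defined, so the comparison can be biased and observed Visit 2 data are left out

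*Combined protocol and SAP*

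**What the plan says.** The rule appears three times. Section 5.4.2 gives the consequence of early discontinuation: "then the collected data will be evaluated but not included in the analysis and a replacement subject will be enrolled in the study". Section 6.1.9 has the same trigger, "If a participant discontinues the study for any reason prior to 3-month visit", and so does section 10.2.1 under randomisation and masking, "If subject discontinues the study for any reason prior to 3-month visit". Randomisation, aspiration and injection all take place at Visit 1 (sections 7.3.1 and 7.3.2), so the rule applies to randomised and normally dosed patients.

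There are several ways out of the study:

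- Section 5.4.1 lets the investigator end participation for an adverse event or other condition "such that continued participation in the study would not be in the best interest of the participant".
- Under section 5.4.2 a patient may leave on request, or "may be withdrawn at any time at the discretion of the Investigator for due to safety or scientific reasons". The same section adds: "Reasons for discontinuation from the study at any time point will be collected".
- Section 10.2.3 covers code-breaking for clinical care, for example after an adverse event: "then the principal investigator will break the code and the subject will be withdrawn from the study".

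On analysis, section 10.1.1 names tests but no analysis set and no method for missing data. Section 10.1.2, headed as the primary efficacy analysis, holds only a safety review and stopping criteria. Section 10.1.3, on the secondary endpoints, is marked as not applicable.

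**The concern.** Randomisation makes the arms comparable only if the patients compared are the patients randomised. A rule that removes patients for what happens after the injection can undo this, and enrolling replacements restores the number but not the comparability. The plan offers no all-randomised analysis alongside.

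The cut-off is also tied to a visit that does not exist. Who is in the efficacy comparison would have to be settled during the trial, case by case.

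Finally, the rule reaches back. It removes measurements already taken from patients who leave later, including Visit 2 KOOS and biomarkers at surgery. The latter are a named secondary endpoint (section 4.2.2).

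**Working it through.** **1. Can the cut-off be applied?** The visits in sections 7.3.1 and 7.3.2 are Visit 1 (1-28 days after injury), "Visit 2 (day of surgery or 4-6 weeks post injury"), Visit 3 (4-14 days after Visit 2), Visit 4 (6 months after Visit 2), Visit 5 (12 months) and Visit 6 (24 months). Nothing falls at three months. The rule does not say whether to count from injury, injection or surgery, and surgery day has no window. The same patient could be in or out depending on the reading.

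**2. What is lost, by time of exit?**

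| Exit | Data already observed and left out of the comparison |
|---|---|
| Before Visit 2 | Baseline only |
| After Visit 2, before the cut-off | Visit 1 and Visit 2 KOOS; Visit 2 serum and urine biomarkers; Visit 2 synovial fluid biomarkers if the patient had surgery |

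Synovial fluid is limited to surgical patients because section 7.1.1 and footnote a of the schedule omit the Visit 2 aspiration for those who decline reconstruction.

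**3. How large could the shift be?** The plan gives no figure to reproduce. Let p be the excess proportion excluded in one arm, and gap the difference in mean outcome between retained and excluded patients. The all-randomised mean is (1 − p) × retained mean + p × excluded mean. Therefore

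shift = retained mean − all-randomised mean = p × gap.

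Both inputs are assumptions.

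| Excess exclusions in one arm | p | Shift, gap 0.5 SD | Shift, gap 1 SD |
|---|---|---|---|
| 1 of 20 | 0.05 | 0.025 SD | 0.05 SD |
| 2 of 20 | 0.10 | 0.05 SD | 0.10 SD |
| 3 of 20 | 0.15 | 0.075 SD | 0.15 SD |
| 4 of 20 | 0.20 | 0.10 SD | 0.20 SD |

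If exclusion is unrelated to outcome, the gap is 0 and so is the shift. If exclusion is equal and for the same causes in both arms, the two shifts cancel.

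As a check on replacement, trials with no true effect were simulated (100,000 per scenario), with exclusions in the active arm only and replacement back to 20. Two exclusions gave a bias of 0.08 SD (correlation of exit with poor outcome 0.5) and 0.17 SD (correlation 1, the extreme), with two-sided type I error of 6.1% and 9.8%. At correlation 0 there was no bias and the error stayed at about 5%. Replacement does not remove the bias.

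No conversion to KOOS points is made. The only SDs in section 10.1.1 are for KOOS Quality of Life, while the primary endpoint in section 4.2.1 is KOOS-Symptoms.

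**4. How much of the shift comes from the rule?** For Visit 2 measures already collected, all of it: keeping the data removes it. For one-year KOOS the answer depends on why patients leave. Suppose those who leave have a Visit 2 score and the analysis uses it.

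- If exit depends only on the Visit 2 score, the shift is removed.
- If exit depends on the one-year score itself, roughly 1 − ρ² of the shift remains, where ρ is the assumed correlation between Visit 2 and one-year scores: 1 − 0.3² = 0.91 and 1 − 0.7² = 0.51. Simulation gives about 92% and 52%.

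**5. Precision.** With 18 instead of 20 scored per arm, the standard error is multiplied by √(20/18) = 1.054, about 5% higher.

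**The case against.** The strongest reply concerns the primary endpoint. Treatment is a single injection at Visit 1 and power is set at one year. A patient who leaves in the first months will usually have no one-year KOOS under any analysis set, so much of the possible bias is ordinary dropout. This stands, and step 4 shows it. It limits what deleting the rule achieves for one-year KOOS, but it does not justify the rule, and it does not apply to Visit 2 measures.

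A second reply is that the data are to be evaluated, so nothing is thrown away. The word is not defined and a separate review is possible. The sentence nevertheless keeps these patients out of the analysis.

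A reader might also infer that the cut-off always falls well after Visit 2, so that every early leaver loses a full set of Visit 2 data. The documents do not support this. Visit 2 is surgery day or 4-6 weeks after injury, and surgery day has no window. Some patients will leave before Visit 2, and those without reconstruction have no Visit 2 synovial fluid.

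Two reassurances in the other direction fail as well. Section 2.1 reports no loss to follow-up in the earlier ACL trial, but that trial had only just completed enrolment, and loss to follow-up is narrower than discontinuation for any reason. Section 8.6 has the safety board review dropouts but does not say they are shown by arm, so an imbalance would not necessarily be noticed.

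**Conclusion.** The point holds. Randomised patients are removed from the comparison by a cut-off that cannot be applied as written, with no all-randomised set to fall back on, and some observed Visit 2 data are left out with them. The comparison can be biased, in a direction that cannot be predicted.

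The size is illustrative: about 0.025 to 0.20 SD for 1 to 4 of 20 excess exclusions in one arm and an outcome gap of 0.5 to 1 SD. Both inputs are assumed. A reader might infer that the result will be biased, or biased by a lot. The documents support neither: they give no exclusion rates or outcome gaps, and exclusions unrelated to outcome, or balanced in rate and cause, produce no bias. The case for change rests on the rule itself and not on a large expected shift.

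**What to change.** 1. Delete the exclude-and-replace sentence in sections 5.4.2, 6.1.9 and 10.2.1. In section 10.1, define the primary efficacy set as all randomised patients in their assigned arm, using all KOOS collected. Keep all observed Visit 2 biomarkers in the secondary analysis.
2. State in sections 5.4.1, 5.4.2 and 10.2.3 that stopping study procedures or being unblinded does not by itself end KOOS collection, provided the patient still consents and the best-interest ground in section 5.4.1 does not preclude it. Section 7.1.1 already allows internet and mailed questionnaires, so no visit is needed. This recovers some one-year scores, not necessarily most; patients who withdraw consent will have none.
3. Cover attrition with the allowance already in section 10.1.1 (16 raised to up to 20 per group), within the cap of 40 in section 4.1, and not with replacements.
4. In section 10.1.1, use a KOOS analysis that keeps patients with incomplete visits, for example a likelihood-based repeated-measures model. A completer analysis may stay as a sensitivity analysis if its cut-off is tied to a scheduled visit.

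The cost is wording changes in these sections, a changed KOOS method, and remote questionnaires for willing early leavers. Some one-year scores will be missing and must be modelled, with a small loss of precision (standard error about 5% higher with 18 instead of 20 scored per arm). The clinical grounds for withdrawal and for breaking the code are unaffected.
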